**Ethics Statement**

The study will be conducted in accordance with the *National Statement on Ethical Conduct in Human Research* (2007), the *CPMP/ICH Note for Guidance on Good Clinical Practice* and consistent with the principles that have their origin in the Declaration of Helsinki. Compliance with these standards provides assurance that the rights, safety and well-being of trial participants are respected.

## Summary

Study title:	Benefits of Analysing Brain Biomarkers in perinatal care: a prospective observational cohort study ( BABBIES Trial )
Protocol version	V 1, dated 29/05/2022
Objectives	
Primary objective	1) Provide feasibility data on the testing of umbilical cord blood for NfL and tau
Secondary objectives	

1) Provide a “normal range of plasma NfL and tau” associated with normal healthy deliveries

2) Provide preliminary data linking cord blood NfL and tau to adverse perinatal outcomes

3) Compare cord blood NfL and tau in elective caesarean deliveries to other deliveries involving a period of labour

4) Provide preliminary data linking cord blood NfL and tau to foetal developmental abnormalities

5) Provide preliminary data linking cord blood NfL and tau to abnormalities on intrapartum monitoring (CTG, scalp lactate)

6) Assess the impact of gestational age on plasma NfL and tau

7) Assess the impact of birth weight on plasma NfL and tau

8) Assess the impact of the duration of the 2nd stage of labour on plasma NfL and tau

9) Determine the proportion of consented patients in whom inadequate cord blood is not collected

Study design	Prospective observational cohort study
Planned sample size	110
Selection criteria	Caesarean deliveries and deliveries involving a period of labour
Study procedure	Umbilical artery and vein cord blood samples (3mL) will be obtained from births at RPAH by the midwife (when feasible)
Statistical considerations	A sample size of 92 placentae (24 elective caesareans, 68 laboured deliveries) is required to ensure that the value for the mean plasma NfL has a 95% confidence interval not exceeding 3pg/mL, with an added 20% (18 patients) to account for issues with biospecimen collection and storage and non-healthy deliveries.
Duration of the Study	6 months

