## 2. HYPOTHESIS

We hypothesise that the range of the 95% confidence interval for the true mean of plasma NfL will be <3pg/mL in the 110 umbilical cord blood samples.

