### 4.4. ENDPOINTS

#### PRIMARY ENDPOINTS

95% confidence interval for mean umbilical cord plasma NfL of 3pg/mL or less

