## 8. STATISTICAL CONSIDERATIONS

### 8.1. SAMPLE SIZE OR POWER CALCULATION

On the basis of preliminary data showing that umbilical cord blood NfL is significantly lower in placentae of women undergoing elective caesarean than women who underwent laboured delivery, we decided to analyse these two populations separately. Based on one study of NfL in cord blood, we anticipate the interquartile range (IQR) of umbilical vein NfL in non-elective caesarean deliveries to be 17pg/mL. We converted this to a standard deviation (SD) using the rule of thumb  $SD = IQR/1.35$ . To ensure that the 95% confidence interval (CI) of the estimate of the true mean does not exceed 3pg/mL, we calculated a required sample size of 68 patients. An additional 12 patients were added to account for issues with biospecimen collection and unforeseen emergencies that make collection unfeasible, for a total of 80 patients. For deliveries that were elective caesarean sections, based on another study that delineated caesarean sections from vaginal deliveries, we estimated the IQR to be 10pg/mL. This results in a sample of 24 participants required to establish a 95%CI of 3pg/mL for the true population mean. We increased this to 30 patients to account for issues with blood collection and storage. The total sample size including all modes of delivery is therefore 110. We will include consented patients in whom an adequate sample of cord blood is unable to be obtained in the 110 participants, in order to inform the feasibility and sample size calculation of a future study. However, given the NfL/tau concentrations will not be obtained, these patients will be omitted from the analysis.

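### The primary NfL mean is defined over inconsistent populations, and the 18 extra patients have two different purposes, so 68 + 24 healthy evaluable samples are not assured

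*Protocol*

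**What the plan says.** Five places in the Protocol bear on the population behind the primary mean.

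- **Section 2 (Hypothesis)** concerns a single confidence interval for a single mean "in the 110 umbilical cord blood samples".
- **Section 4.4 (Primary endpoints)** gives "95% confidence interval for mean umbilical cord plasma NfL of 3pg/mL or less" and names no population.
- **Section 8.1**, citing a reported NfL difference between elective caesarean and laboured births, says "we decided to analyse these two populations separately". It derives 68 and 24 and raises them to 80 and 30. The reason for the first increase is: "An additional 12 patients were added to account for issues with biospecimen collection and unforeseen emergencies that make collection unfeasible". The reason for the second (6 patients) is blood collection and storage. Women without an adequate sample are counted in the 110, but "given the NfL/tau concentrations will not be obtained, these patients will be omitted from the analysis". Section 8.2 keeps the split, with initial analyses run separately for elective caesareans and for all other deliveries.
- **The Summary** (Statistical considerations) repeats 24 + 68 = 92 and describes the increase as "with an added 20% (18 patients) to account for issues with biospecimen collection and storage and non-healthy deliveries".
- **Section 7.1** makes every birth by emergency caesarean non-healthy, together with several other neonatal events. **Section 6.1** makes all births eligible.

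**The concern.** There are two linked problems.

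First, the primary result depends on which sentence is followed. A pooled mean and two stratum means are different quantities with different precision. If the strata differ, as section 8.1 expects, a pooled mean also depends on the 80:30 enrolment mix. The Hypothesis refers to 110 samples, yet section 8.1 allows some of the 110 participants to have none, so that number of samples will not exist if any collection fails.

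Second, an allowance for non-healthy deliveries has a clear function only if such births do not count towards the 92. Read that way, the Summary implies a healthy-only 92. Section 8.1 never mentions health status and has already given all 18 patients to samples that cannot be obtained. A birth that is non-healthy but successfully sampled is covered in the Summary and not in section 8.1.

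At stake is whether the precision criterion is judged on a population fixed in advance. Left open, the population could be settled after it is known which one meets 3 pg/mL.

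**Working it through.** **Inputs (section 8.1).** IQR 17 pg/mL for births other than elective caesarean; IQR 10 pg/mL for elective caesarean; SD = IQR/1.35; 95% interval; target 3 pg/mL; 68 raised to 80 and 24 raised to 30.

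**1. Reproduce the plan's figures.** n = (1.96 × SD / h)², rounded up, with h the half-width.

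- Laboured: SD = 17/1.35 = 12.59; with h = 3, n = 67.7, so 68.
- Elective: SD = 10/1.35 = 7.41; with h = 3, n = 23.4, so 24.

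Both match. With 3 as the full width (h = 1.5) the formula gives 271 and 94, so the plan's sizes correspond to a half-width of 3.

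**2. What the allowance absorbs, from all causes together.**

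- Laboured: 12/80 = 15.0%.
- Elective: 6/30 = 20.0%.
- Overall: 18/110 = 16.4%.

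As an add-on, 18/92 = 19.6%, which agrees with the Summary's 20%.

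**3. Pooled versus stratified precision.** For 80 + 30 samples, the within-stratum variance is (80 × 12.59² + 30 × 7.41²)/110, giving an SD of 11.41 and a half-width of 1.96 × 11.41/√110 = 2.13. The Protocol does not state the gap between stratum means. Assuming 0 to 15 pg/mL, the pooled SD runs from 11.41 to 13.23, the half-width from 2.13 to 2.47 and the full width from about 4.3 to 4.9. The stratum half-widths are 2.99 (n = 68) and 2.96 (n = 24).

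**4. If only healthy births count.** The Protocol gives neither a sample-failure rate (f) nor a non-healthy rate (u). The rates below are assumptions, taken as independent and equal in both strata, with the planned SDs applied to healthy births. Expected evaluable n = enrolled × (1 − f)(1 − u); the probability is binomial.

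| f | u | Laboured n of 80 (half-width) | P(at least 68) | Elective n of 30 (half-width) | P(at least 24) |
|---|---|---|---|---|---|
| 5% | 10% | 68.4 (2.98) | 0.63 | 25.6 (2.87) | 0.87 |
| 10% | 10% | 64.8 (3.07) | 0.22 | 24.3 (2.95) | 0.66 |
| 10% | 20% | 57.6 (3.25) | 0.005 | 21.6 (3.12) | 0.22 |

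If collection failures alone use up the 15% and 20%, exactly 68 and 24 remain, and any exclusion of non-healthy births then causes a shortfall. Emergency caesareans, all non-healthy under section 7.1, fall in the laboured stratum, which has the smaller proportional allowance.

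**The case against.** The best defence is that the stratified plan is already clear. Sections 8.1 and 8.2 both separate the strata, the Summary itself gives 24 + 68, and section 8.1 expressly drops women without a sample. On that view the 110 samples in the Hypothesis are loose wording, and the Summary's non-healthy deliveries loosely paraphrase section 8.1's emergencies. Section 6.1 offers category 1 emergency caesareans as an example of infeasible collection, and section 7.1 makes them non-healthy, so the two reasons overlap.

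Much of this stands. No analysis section describes a pooled mean, and the overlap is real. But the Hypothesis and the primary endpoint are where the criterion is stated, and neither reflects the split. The paraphrase reading also leaves out births that are non-healthy and sampled.

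Three stronger readings are tempting, and the documents do not support them.

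- **That the 18 cannot deliver 68 + 24.** Without a failure rate or a non-healthy rate this is not shown: 5% and 10% would meet both targets in expectation.
- **That the primary population is healthy births.** This is inferred from one Summary phrase. Section 4.4 places healthy births under a secondary endpoint, and section 6.1 admits all births.
- **That the Summary's 20% is an error because 110 × 0.8 = 88 is below 92.** The Summary describes an addition, not a tolerated loss, and 19.6% is right for an addition.

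**Conclusion.** The inconsistency is in the text and needs no assumption: one mean over 110 samples in section 2, one mean with no population in section 4.4, two separately analysed strata in sections 8.1 and 8.2, and an allowance that the Summary and section 8.1 explain differently. It affects the primary criterion, since the half-width is about 3 pg/mL per stratum but about 2.1 to 2.5 pg/mL if 110 samples were pooled (assuming a gap between stratum means of 0 to 15 pg/mL).

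The consequence for healthy births is conditional. The plan tolerates 15% and 20% total loss, so 68 + 24 healthy evaluable samples are not assured. The shortfall is modest in the illustrated cases: laboured half-widths of 3.07 and 3.25 against a target of 3. A reader might extend this to a healthy-only precision of 3.3 to 3.9 pg/mL, but that needs an assumed 30% to 50% loss and covers the laboured stratum only. Section 8.1 also does not say whether its IQR of 17 describes healthy births or all births, so every healthy-only figure here carries that SD as an assumption.

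**What to change.** 1. Restate the Hypothesis and the primary endpoint as two stratum-specific means (elective caesarean; all other births) in participants with a valid NfL result, matching sections 8.1 and 8.2. Remove the reference to 110 samples and keep 110 as the number of participants.
2. Give the 18 extra patients one purpose in both the Summary and section 8.1. Either delete the Summary's mention of non-healthy deliveries, so that the primary means cover all births with a result (consistent with sections 6.1 and 8.1), or, if healthy births are intended, say so and restate the achievable precision with the loss rate assumed. The choice is the sponsor's.
3. State the tolerated loss as 15% (80 to 68) and 20% (30 to 24).
4. State that 68 and 24 correspond to a half-width of 3 pg/mL, and word section 2 to match.
5. Do not enter a fixed healthy-only precision such as 3.3 to 3.9 pg/mL, which would rest on assumed losses.

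The cost is wording only, with no extra patients. The drawback is that the stated precision for healthy births may become less favourable.

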## 1. BACKGROUND AND INTRODUCTION

### 1.1. DISEASE/PROPOSED INTERVENTION BACKGROUND

Hypoxic–ischaemic encephalopathy (HIE) is a common cause of neonatal encephalopathy (NE), affecting 1–2 in every 1000 live births. Approximately 60% of those with moderate–severe HIE will die in the neonatal period, and one quarter of those who survive will experience long-term neurocognitive deficits.

Therapeutic hypothermia is the mainstay of treatment in moderate and severe HIE. If applied appropriately, it increases the rate of survival with normal neurological outcome at 18 months from 24% to 40% (relative risk: 1.63, 95%CI: 1.36–1.95). Early identification of possible HIE is crucial, as hypothermia must be induced within 6 hours post-delivery; so critical is this time window that definitions of HIE severity have evolved over time to reflect this urgency of diagnosis. However, identifying at-risk neonates is difficult, because current practice relies on clinical signs, cardiocography and acid-base monitoring all of which are limited in their sensitivity in HIE detection. Furthermore, the manifestation of clinical signs is significantly influenced by the timing of the hypoxic insult, with recent hypoxia more likely to be subclinical, allowing the neonate with early HIE to slip undetected through the 6-hour detection time-limit. The shortcomings of current HIE detection methods are in part because none of them detect neuronal injury directly. Neuronal injury biomarkers may have prognostic significance and assist with patient selection for future neuroprotective HIE therapies.

It was traditionally believed that neonates with mild HIE have comparable long-term neurological function to their non-encephalopathic counterparts. However, recent evidence suggests that HIE severity and long-term outcome may exist on a continuum. Mild HIE cases are more difficult to detect using current clinical criteria, and may actually represent an evolving HIE due to a recent hypoxic insult. Biomarkers may help identify such patients who will benefit from therapeutic hypothermia despite being classified as having ‘mild’ HIE as per current clinical criteria, which will need to be assessed in future clinical trials.

Biomarkers of neuronal injury obtained from umbilical cord blood represent a tantalising addition to the toolkit for HIE detection and risk stratification. Many plasma and cerebrospinal fluid (CSF) biomarkers obtained in the hours and days post-delivery have been shown to be elevated in HIE compared to controls; however, the time delay to obtain serum or CSF samples from a neonate risks jeopardising eligibility for therapeutic hypothermia. Studies of umbilical cord blood biomarkers in HIE have been scarcer than those of neonatal plasma biomarkers, but the findings are nonetheless promising. We propose that monitoring the neuronal injury biomarkers, neurofilament light (NfL) and tau, may prove a useful decision aid in peripartum care.

Neurofilament light is a structural protein of neurons that is released at the time of many types of neuronal injuries, ranging from ischemia (e.g., stroke), to inflammation (e.g., surgery or multiple sclerosis) or dementia (e.g., Alzheimer’s disease). We have conducted a systematic review and identified two observational studies that have shown that NfL is raised in the umbilical cord blood of babies with adverse perinatal outcomes compared to healthy babies. Toorell et al. found that the level of NfL in the umbilical cord blood was 39.2 pg/mL in 10 neonates with asphyxia compared to 23.3 pg/mL in 18 healthy controls (p=0.016). Depoorter et al. showed that the level of NfL in the umbilical cord blood was inversely correlated with body weight, gestational age, and 5- and 10-min APGAR scores in a cohort of 203 term and preterm neonates. A published abstract (with no full-text article) also demonstrated that levels of cord blood NfL were lower in neonates delivered in the context of an elective caesarean section than those born via a vaginal delivery. These findings are

supported by studies of CSF NfL in asphyxia as well as those from neonatal intensive care. Altogether, these studies support NfL as a predictive biomarker of HIE and perinatal morbidity.

Tau is a phosphoprotein critical to microtubule stability in neuronal axons that is released into the bloodstream in the setting of CNS injury. Tau has been shown to be elevated in blood of patients with various neurodegenerative diseases, brain metastases, and obstructive sleep apnoea. Our systematic review revealed three studies that analysed plasma tau levels in umbilical cord blood. Turc et al. found that umbilical cord blood tau was lower in neonates delivered by caesarean section rather than vaginal deliveries. Another study has shown that levels of tau in the cord blood are higher in very-low birth weight (VLBW) neonates with foetal growth restriction (FGR) compared to VLBW neonates without FGR, but this difference between groups was not present in serum samples from days 1–5 of life. Toorell et al, who also looked at NfL, noted a higher plasma tau concentration in 10 neonates with intrapartum asphyxia compared to 18 healthy neonates (48.0 vs. 11.7pg/mL, p=0.03). Together, these findings suggest that umbilical cord blood tau may be reflective of perinatal stress and neuropathology.

We propose to test whether collection of umbilical cord blood is feasible at RPA, as a forerunner for clinical trials in the use of NfL and tau as a decision aid in obstetric care, as a prognostic outcome in neonatology, or as a probe to study the safety of obstetric anaesthesia approaches.

## 1.2. RATIONALE FOR PERFORMING THE STUDY

Any approach to reduce the burden of adverse perinatal outcomes would be a major advance. A decision aid that directly measures brain injury could represent a major advance over current indirect approaches, such as measuring CTG or scalp lactate. In the future, we hope to develop a point-of-care NfL and tau measure that may be used as an adjunct or as a replacement to scalp lactate testing of the foetus, for decisions in labour ward regarding the optimal timing of delivery.

Our focus is on improving perinatal outcomes. A better decision-making aid may enhance:

1. De-escalation of care through confirming the baby is healthy
2. Escalation of obstetric care in a vulnerable baby
3. Understanding the treatment needs in neonatology
4. Improving the safety of anaesthetic care

This study will provide feasibility for a district-wide research cohort study of NfL and tau cord blood levels and perinatal outcomes. A Sydney-based NfL-SIMOA service is being developed in Sydney and with academic and industry partners we will develop a point-of-care testing device for use across peripartum units.

## 2. HYPOTHESIS

We hypothesise that the range of the 95% confidence interval for the true mean of plasma NfL will be <3pg/mL in the 110 umbilical cord blood samples.

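### The hypothesis asks for a 95% CI range below 3 pg/mL, but the sample sizes of 68 and 24 follow only if 3 pg/mL is the half-width

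*Protocol*

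**What the plan says.** The 3 pg/mL figure appears in four places in the protocol.

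- **Section 2 (Hypothesis):** "the range of the 95% confidence interval for the true mean of plasma NfL will be <3pg/mL in the 110 umbilical cord blood samples".
- **Section 4.4 (Primary endpoints):** "95% confidence interval for mean umbilical cord plasma NfL of 3pg/mL or less".
- **Summary (Statistical considerations):** the 92 placentae are the number that "is required to ensure that the value for the mean plasma NfL has a 95% confidence interval not exceeding 3pg/mL".
- **Section 8.1 (Sample size):** "To ensure that the 95% confidence interval (CI) of the estimate of the true mean does not exceed 3pg/mL", 68 patients are required in the laboured group. For elective caesareans, "This results in a sample of 24 participants required to establish a 95%CI of 3pg/mL for the true population mean".

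Section 8.1 sizes the two delivery groups separately and says they will be analysed separately. It raises 68 to 80 and 24 to 30 for collection problems, giving 110. Consented participants without an adequate sample count towards the 110 but are left out of the analysis.

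Only section 2 says which feature of the interval is meant. The other three places give a confidence interval of a certain size without saying whether that is the full width or the half-width. Plus-or-minus, half-width and margin of error appear nowhere.

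**The concern.** The same 3 pg/mL serves as the study's only hypothesis, its only primary endpoint and the target of its sample size calculation. If section 2 means the full width and section 8.1 used the half-width, the study has been sized for a precision half as tight as the one it hypothesises. Because required n varies with the inverse square of the width, that is a four-fold difference in sample size.

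The endpoint is a threshold, so the ambiguity decides whether the study reports success. If it is settled only after the data are seen, the primary criterion will have been chosen with knowledge of the result. Section 8.1 also says the study should inform the sample size of a future study, so a misdescribed precision could carry forward.

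**Working it through.** **Inputs (section 8.1).** IQR 17 pg/mL for deliveries other than elective caesarean ("we anticipate the interquartile range (IQR) of umbilical vein NfL in non-elective caesarean deliveries to be 17pg/mL"), IQR 10 pg/mL for elective caesarean, SD = IQR/1.35, 95% confidence, target 3 pg/mL. Enrolment is 80 and 30.

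SD, laboured: 17/1.35 = 12.59. SD, elective caesarean: 10/1.35 = 7.41.

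**1. Reproducing the plan's figures.** For one mean, n = (1.96 × SD / h)², where h is the half-width.

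| Reading of 3 pg/mL | h | Laboured | Elective caesarean |
|---|---|---|---|
| Half-width | 3 | 67.7, so 68 | 23.4, so 24 |
| Full width | 1.5 | 270.7, so 271 | 93.7, so 94 |

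The stated 68 and 24 match the half-width reading exactly. One-sided z does not reproduce them either: it gives 48 and 17 with h = 3, and 191 and 66 with h = 1.5. The full-width reading needs 271 + 94 = 365 analysable samples, against 68 + 24 = 92.

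**2. Full width that the design delivers.** Width = 2 × multiplier × SD / √n, in pg/mL.

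| Stratum | n | z-based | t-based |
|---|---|---|---|
| Laboured | 68 | 5.99 | 6.10 |
| Laboured | 80 | 5.52 | 5.60 |
| Elective caesarean | 24 | 5.93 | 6.26 |
| Elective caesarean | 30 | 5.30 | 5.53 |

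**3. One pooled mean over the 110 samples that section 2 names.** The documents do not give the mean difference between strata, so I take 0 to 10 pg/mL as an assumption. The pooled SD at 80:30 is 11.38, 11.60 and 12.23 for differences of 0, 5 and 10. The t-based full widths at n = 110 are 4.30, 4.38 and 4.62. This assumes that all 110 samples are analysable. With 92 analysable, the widths are 4.73 to 5.07.

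**4. Chance of meeting each criterion.** The observed half-width is t × s / √n. For normal data, (n − 1)s²/SD² is chi-squared on n − 1 degrees of freedom, so P(half-width ≤ h) = P(χ² ≤ (n − 1) × n × h² / (t² × SD²)).

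| Stratum | n | P(full width ≤ 3) | P(half-width ≤ 3) |
|---|---|---|---|
| Laboured | 68 | below 10⁻¹⁰ | 0.45 |
| Laboured | 80 | below 10⁻¹⁰ | 0.82 |
| Elective caesarean | 24 | below 0.0001 | 0.43 |
| Elective caesarean | 30 | below 0.0001 | 0.76 |

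For the pooled 110, a full width of 3 would need an observed SD of 3 × √110 / (2 × 1.982) = 7.94, against an expected 11.38 or more.

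**5. How far 68 and 24 secure a half-width of 3.** With t in place of z, the expected half-widths are 1.996 × 12.59/√68 = 3.05 and 2.069 × 7.41/√24 = 3.13, slightly over the target. At 80 and 30 they are 2.80 and 2.77.

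**The case against.** The strongest reply is that a confidence interval of 3 is loose shorthand for plus or minus 3. The exact match of 68 and 24 to that reading suggests it is what the authors intended, and at 80 and 30 the expected half-widths are inside 3.

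Much of this stands. Only section 2 says range. A reader might infer that the primary endpoint itself demands a full width of 3 or less, so that the trial is bound to fail. Section 4.4 does not support that: its wording, like that of the Summary and section 8.1, fits either reading. It is also fair that the full width is about twice 3 only at 68 and 24. At 80 and 30 without losses it is about 1.8 times (5.5/3), and for the pooled 110 about 1.4 to 1.5 times (4.3/3 to 4.6/3). Finally, this is an observational cohort with a feasibility objective, and no go/no-go rule is attached to the criterion. Missing it would not affect patient care or the validity of the data.

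The reply does not remove the conflict. If plus or minus 3 was meant, section 2 states the wrong quantity; if section 2 is right, the sample size is about a quarter of what is needed.

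**Conclusion.** The concern holds as a contradiction between section 2 and section 8.1, with the Summary and section 4.4 left ambiguous. On every reading examined, the full width exceeds 3 pg/mL: about 6 per stratum at 68 and 24, about 5.5 at 80 and 30, and about 4.3 to 4.6 pooled over 110. The criterion as worded in section 2 will almost certainly be missed even if every planning assumption is right. On the half-width reading the planned enrolment is reasonable, though it does not guarantee the target.

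There is a second, smaller conflict. Section 2 speaks of one mean in 110 samples, while section 8.1 sizes two strata separately and omits participants without a sample.

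A reader might also infer that the analysable targets should rise to the t-based 71 and 26. I would not ask for that. With enrolment fixed, it cuts the loss allowance from 12/80 = 15% to 9/80 = 11%, and from 6/30 = 20% to 4/30 = 13%. The chance of an observed half-width of 3 or less would still be only about 0.55 per stratum.

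These conclusions rest on the protocol's IQRs and its IQR/1.35 conversion. The probabilities also assume normal data and no losses at the stated n. The pooled range rests on the assumed mean difference of 0 to 10 pg/mL.

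**What to change.** Restate the criterion identically in the Summary and in sections 2, 4.4 and 8.1: a half-width (margin of error) of 3 pg/mL for mean NfL, that is, a 95% CI about 6 pg/mL wide, applied separately to elective caesarean and to all other births. In section 2, remove the reference to a single interval over 110 samples.

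Keep enrolment at 80 and 30. In section 8.1 and the Summary, describe 68 and 24 as z-based planning figures for the expected half-width, and drop the claim that they ensure it. It would help to state the chance of an observed half-width of 3 or less: about 0.82 and 0.76 at 80 and 30 with no losses, and about 0.45 and 0.43 at 68 and 24.

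This is a wording amendment, to be made before the primary endpoint is evaluated. Its cost is that the stated precision becomes less favourable. If the sponsor really wants a full width of 3 pg/mL per stratum, the alternative is about 271 + 94 analysable samples before any allowance for losses.
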